Overall tolerance and safety: WCE is safe in children approximately 9 years of age and older, endoscopic placement is feasible in individuals refusing or unable to swallow the capsule but adds to the potential morbidity and expense of the procedure. WCE has been safely performed in children as small as 11.5 kg [4]. Jensen and colleagues studied the factors associated with incomplete WCE studies and their diagnostic yield in pediatric patients. In this study, 22% of the WCE studies were incomplete, and in 12 (44%) of these were normal pre-WCE radiologic findings [4].

WCE should be used with caution and most likely contraindicated in patients with known swallowing disorders, gastrointestinal obstruction and fistulas. The risk for WCE retention (which is defined as capsule remains in digestive tract for a minimum of 2 weeks or it requires direct intervention to aid in its passage) in Crohn's disease patients is estimated to be 5%–13% [12]. Even though Crohn's disease is reported to have the most

common retention rate it is reported in metanalysis that retention rate is 2.6% in all prospective and retrospective studies [13].

Atay and colleagues investigated the risk factors for capsule retention in their cohort (n = 207) of pediatric patients studied by WCE[14]. Capsule retention complicated 1.4% of studies; all in known Crohn's patients. The risk in known CD patients was therefore 5.2%, and rose to 37% if there had been a prior small bowel series showing small bowel disease, and to 43% if the patient's body mass index was less than the 5th percentile, presumably indicative of more severe, longstanding small bowel involvement [14].

The Patency Capsule (Agile ®) was developed, tested, and shown to greatly curtail the possibility of small bowel capsule retention and therefore obviate the need for surgery[15]. A pre-WCE, patency capsule (PC) strategy has completely removed the incidence of capsule retention[15]. The caveat to PC testing is that it also impacts the utility of WCE overall in so far as a proportion of patients cannot thus be studied (failed PC passage). The Patency capsule is identical in shape and size to the actual WCE device but in the presence of small intestinal enzymes it will dissolve starting at 30 hours post ingestion, thus slow passage or retention of PC in the small bowel signals a risk of capsule retention and are usually interpreted as a contraindication for WCE.[16]

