with a parent/caregiver at school during the lunch period. The patient or caregiver must record the exact time the pill is swallowed to calculate

time till x-ray. This will allow for the subsequent miralax dose and any necessary x-rays to take place after school hours.

- Subjects should not be around electromagnetic fields while PC procedure is performed
- Subject will receive Miralax and instructions for WCE home prep.
- Post Patency Capsule Swallow
 - A follow up phone call will take place with the subject and family the day following patency capsule ingestion. Subjects will return to CM radiology for an abdominal x-ray within 28-40 hours, as close as possible to 30 hours after swallowing the patency capsule unless they report to the study team that they visibly saw the excreted capsule. If the patency capsule has passed through the bowel then the subject will continue with WCE procedures.
 - *The study doctor or the subjects regular GI doctor or an appropriate delegate will discuss the results of MRE and patency capsule with the subject and guardian to decide if is a possible increased risk of retention and families will be able to decide if they would like to continue with study procedures. GI providers will be added to the MARS electronic IRB submission form and listed as study staff when they refer a subject so they are identified as being able to participate in these study procedures.*
- WCE Visit
 - The subject will return to the GI clinic to complete the WCE 5 days (\pm 2 days) from the time of patency capsule ingestion. Subject dietary restrictions the day before the wireless capsule endoscopy (WCE) visit.
 - To allow for greater flexibility for those subjects who are in school at the time of study procedures. The miralax prep may be started after school however the no solid foods after noon must still be observed.
 - Subject will fast for 8 hours overnight.
 - WCE visit (approximately 1 hour) - performed as a part of the research study.
 - The WCE used in this study is the PillCam SB video capsule (Given Imaging, Israel) that measures 11mm \times 26mm and weighs less than 4 g.
 - Subjects will wear a belt sensor around their waist and a recording device attached to it for the duration of the WCE study. device

- Subject will be asked questions about any symptoms and/or new medications.
- Subject will swallow the capsule in GI procedure room.
- Subjects should not be around electromagnetic fields while WCE procedure is performed

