- Subject may drink clear liquids 3 hours after ingesting the capsule
- Subject may eat solid foods 6 hours after ingesting the capsule, respectively.
- Subjects will be asked to return to the GI procedure room to return the belt sensor 8-12 hours after ingesting the WCE

At times due to Crohn's disease a portion of the bowel can become inflamed and narrowed. These stenosed/strictured areas are not often easily identified until a patient has symptoms of bowel obstruction. It is possible that the capsule may identify these areas because it is not able to pass through the decreased space in the lumen. If the family or subject does not visually see the capsule pass within 2 weeks from the time of capsule ingestion, then an x-ray will be performed to assess if it is retained in the bowel. If the capsule is retained, the PI or Sub-I will notify the subject's primary GI physician about the finding and medical management will be attempted to reduce the subject's inflammation so that the capsule may pass through. In some cases the capsule may identify such a diseased portion of the bowel that it needs to be surgically removed. This capsule retention due to a strictured portion of the bowel will not be considered an adverse event. It will be considered an incidental finding of the subject's disease process. The subject and their 3rd party payor will be responsible for the treatment of these incidental findings.

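### Section 5 rules in advance that stricture-related retention of the research capsule is not an adverse event, which keeps a known harm of the study procedure out of the adverse-event record

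*Combined protocol and SAP*

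**What the plan says.** The magnetic resonance enterography (MRE) is standard of care (Section 4, inclusion criteria). The capsule examination is not; Section 5 describes it as: "WCE visit (approximately 1 hour) - performed as a part of the research study".

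If the capsule is not seen to pass within 2 weeks, Section 5 calls for an x-ray. If it is retained, the subject's gastroenterologist is told and medical treatment of the inflammation is tried so that the capsule can move on. The text then continues: "In some cases the capsule may identify such a diseased portion of the bowel that it needs to be surgically removed". The next sentence is the rule at issue: "This capsule retention due to a strictured portion of the bowel will not be considered an adverse event". Two consequences follow: "It will be considered an incidental finding of the subject's disease process", and "The subject and their 3rd party payor will be responsible for the treatment of these incidental findings".

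Section 2 defines retention: "capsule remains in digestive tract for a minimum of 2 weeks or it requires direct intervention to aid in its passage". Of a cited pediatric cohort it says: "Capsule retention complicated 1.4% of studies; all in known Crohn's patients".

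Section 8 lists two relevant measures. Measure 3 compares the complication rate of WCE with that of the first radiologic test. Measure 4 is the WCE retention rate. Complication is not defined, the Section 5 rule is not mentioned, and the Data Analyses text gives no method for either measure.

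**The concern.** A stricture belongs to the patient's disease. A capsule lodged at that stricture is there only because the study put it there. The Section 5 rule merges the two and settles the classification before any case has been looked at.

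The exempted category is also the central one. Stricture is the only mechanism of retention that Section 5 describes, and everyone enrolled has Crohn's disease or indeterminate colitis. Apart from the literature summary in Section 2, this sentence is the only place in the available text that deals with adverse events, and its content is an exclusion.

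What is at stake is the safety record of a research-only procedure in children. A child whose capsule is retained at a stricture would have no adverse event recorded for it, by definition and not by assessment.

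**Working it through.** The plan states no figure on this point, so there is nothing to reproduce. The check sets the sections side by side and then gives the scale.

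**1. Does the event arise from the study?** Yes. Section 5 makes the WCE a research procedure. It also says that medical treatment after a retention is meant to help the capsule pass, so part of the response is directed at the capsule itself.

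**2. How does the protocol treat retention elsewhere?** Section 2 gives it a definition and describes it as complicating studies. Section 8 makes its rate an outcome. Only the Section 5 sentence removes it from adverse events.

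**3. How far does the exemption reach?** It covers retention due to a stricture. Retention from any other cause is not exempted.

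**4. Where would a stricture-related retention appear if the plan is followed?**

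| Place | Recorded or counted? | Basis |
|---|---|---|
| Detection | Yes | Section 5, x-ray if not seen to pass within 2 weeks |
| Measure 4, retention rate | Yes | Section 8; nothing excludes it |
| Adverse-event record | No | Section 5 exemption |
| Measure 3, complication rate | Not stated | Section 8 does not define complication or cite the rule |

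**5. Scale.** Inputs are the 34 evaluable patients in Section 8 and the retention figures after patency testing in Section 2.

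- One retention: 1/34 = 2.9%. Two: 2/34 = 5.9%. The number who swallow the WCE may differ from 34. With the 40 to be recruited under Section 8 the step would be 1/40 = 2.5 points, and with the 50 named in Section 4 it would be 1/50 = 2.0 points.
- Exact (Clopper-Pearson) 95% intervals: 0/34 gives 0 to 10.3%; 1/34 gives 0.1 to 15.3%.
- Small retrospective series: 1/19 = 5.3%, exact 95% interval 0.1 to 26.0%. Applied to 34 patients this gives 34 × 1/19 = 1.8 expected. The interval limits (0.13% and 26.03%) give 34 × 0.0013 = 0.04 and 34 × 0.2603 = 8.9.
- Trial of 106 patients: no retention once patency was proved. The number who went on to WCE is not given. If it were all 106, the upper 95% limit would be 3.4%, or 34 × 0.0342 = 1.2 in 34.

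These inputs do not support a forecast. The single case in the series led to a new Crohn's diagnosis, whereas this study excludes patients whose IBD diagnosis is not established. The rates cover retention of any cause, and the stricture-related share is not given.

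**The case against.** The strongest reply is that nothing is hidden. Retention is actively looked for, reported to the treating physician and listed as a separate measure. That is correct, and a reader who inferred that retentions would go unreported would be wrong. Measure 4 is a count, however. It does not place the event in the adverse-event record, and it does not capture the intervention that follows.

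A second reply is that retention should be rare, because the capsule is given only after a test: "If the patency capsule has passed through the bowel then the subject will continue with WCE procedures". Section 2 even states that patency testing has eliminated retention, although it also cites the 1 in 19. Rarity limits the size of the problem but does not justify exempting the event in advance.

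Three stronger readings are tempting, and the documents do not support them.

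- **That the capsule causes the need for surgery.** Section 5 gives the diseased bowel as the reason for any resection.
- **That Measure 3 will understate WCE complications.** Section 5 speaks of adverse events and Measure 3 of complications; nothing links the two. The wording in Section 2 rather favours counting retention as a complication. Taken alone, the undefined term is a missing detail.
- **That a reported adverse-event rate would be biased.** Section 8 lists no such rate, so 0/34 against 1/34 only illustrates scale.

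It may also be said that requiring an adverse event every time prejudges the case just as the exemption does. It does not, provided that recording the event and judging its cause are kept as separate steps.

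**Conclusion.** The concern holds in a limited form. The exemption is an explicit rule, and following it leaves stricture-related retention of a research-only capsule out of the adverse-event record, against the protocol's own account of retention in Section 2. Detection, Measure 4 and the primary aim are unaffected. Measure 3 would be affected only if it were read as following the Section 5 label, which the documents do not say.

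Each retention is worth 2.9 percentage points if 34 patients swallow the WCE. The number of such events cannot be predicted from the documents, and if none occurs no result changes. The conclusion rests on the available text; consent pages were removed, so what families are told about retention and payment cannot be judged. The change is worth making because it is cheap and improves safety reporting.

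**What to change.** In Section 5, delete the adverse-event exemption. Record each retention that meets the Section 2 definition as an adverse event, together with any resulting intervention. Assess its relation to the capsule and to the underlying disease case by case. Continue to record the stricture as a disease finding.

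In Section 8, define complication for Measure 3, and state that these retentions count in Measure 3 as well as Measure 4, with all patients who swallowed the WCE as the denominator.

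Once the label changes, check that the sentence on payment for incidental findings still fits.

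Separately, reconcile Sections 3 and 8. Section 3 lets patients with a stenosis or stricture on MRE choose to continue, while Section 8 makes MRE findings contraindicated with WCE screen failures, without saying whether a stricture is one of them. This is a matter of consistency and does not bear on the main point.

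The cost is an IRB amendment to the wording, a short relatedness assessment per event, for which the protocol has no process at present, and possibly a less favourable WCE safety figure. No new examination is needed, because the 2-week x-ray is already planned.

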6. DATA COLLECTION

Data Collection Procedures

- The subject's medical record will be reviewed for data collection to include but not limited to, subject demographics, medical and surgical history, imaging results initial disease presentation and patient current clinical status. Data will be collected on a separate paper data collection form.
- The capsule images will be independently interpreted by the PI initially and then confirmed by two gastroenterologists with 4 - 10 years of experience in capsule endoscopy. The results will be reported in the subject's medical record as they would be for standard of care in compliance with the CMH policy on medical record documentation of research subjects. The subjects regular GI provider will review the results of the WCE and consider the results when making decisions about the subjects treatment plan. We will be using the capsule endoscopy data collection form including the Lewis scoring system that is automatically

calculated and included in the RAPID® software. Lewis score is a WCE ranking of inflammatory activity into three levels based on erythema, stenosis, edema and erosions in small intestinal tertiles: 1) no disease or clinically insignificant disease ($LS < 135$); 2) mild disease ($135 \leq LS \leq 790$); and 3) moderate or severe disease ($LS > 790$).

- The study will be considered negative if no abnormalities were seen and as positive if clear abnormalities of the SB mucosa (i.e. ulcerations, erosions, polyps, vascular lesions, and bleeding lesions) were observed. White lesions within a crater with surrounding erythema were considered ulcers, whereas small superficial white lesions, even with surrounding erythema, were considered erosions. If no abnormalities or non-specific findings (such as erythematous spots or mucosal breaks) were seen the examination was considered non-specific or normal.
- The examiners of WCE and MRE will be blinded to each other's findings but will be aware of the patient's history and laboratory data.
- To reduce variation in MRE readings, one radiologist will retrospectively review the MRE for all subjects to provide a consistent assessment of the extent of the subjects' disease.

Records to be kept

Information will be collected on a paper data collection sheet and entered in an electronic database. Additionally if a research team member chooses they may complete the data collection form electronically by typing results into the electronic word document version of the data collection sheet and saving it to the internal CMH server. Data collection forms will be identified only by assigned subject study ID, date of service and will be retained indefinitely. The electronic database will only retain assigned subject study ID numbers and will be retained indefinitely. An electronic master subject list will include subject name, MRN, dates of service and study assigned ID number. The electronic master subject list will be retained indefinitely. A pre-recruitment log with patient name, MRN and date of MRE will be used to track and keep record of those subjects approached for study participation. The pre-recruitment log will be destroyed at the time enrollment is completed. The WCE procedure uses a software installed on the hard drive of the password protected CMH GI procedure room computer. The images from the study and subject name, MRN, and date of birth will be retained indefinitely on the hard drive. The information entered into the medical record will be retained indefinitely.

Secure Storage of Data

Paper/physical Documents: These documents will be stored in a file cabinet in the locked research room in the GI clinic:

- Signed Permission/Assent/Consent
- Paper Data Collection Forms

Electronic Documents: These documents will be kept on the secure internal CMH server, in a restricted access folder:

- Data Collection form
- Master Participant List
- Pre-recruitment Log
- Data Collection Database

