1. STUDY OBJECTIVES/HYPOTHESIS

Primary Objective(s)

Primary aim: Compare the diagnostic yield of Magnetic Resonance Enterography (MRE) with Small-Bowel Capsule Endoscopy (SBCE) in pediatric patients with known

Inflammatory Bowel Disease (IBD) including Crohn's disease (CD) or indeterminate colitis (IC).

Secondary Objective(s)

1. To determine the detection rate of small bowel disease / complications, subjected to a strategy of Wireless Capsule Endoscopy (WCE) – small bowel screening / surveillance vs MRE in a pediatric tertiary medical institution.
2. Compare sensitivity and specificity of both MRE and WCE in identifying patients with active vs. inactive CD and IC as defined by the Pediatric Crohn's disease activity index.
3. To correlate the findings detected on WCE by Lewis score with Crohn's disease activity index.

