5. STUDY PROCEDURES

- Prior to MRE visit:
 - The provider ordering the MRE will contact a member of the study team to let them know an MRE for a patient has been scheduled.
 - Team members will have the option of calling the parent/authorized representative of the family to ask if they would like to hear about the study. If yes, the team member will explain the study and follow protocol for telephone consent or agree to meet with the family when the patient comes in for his/her MRE.

- Standard of Care MRE visit:
 - At the MRE procedure visit, if not previously consented, the subject and family will be approached by a member of the study team to explain the study and ask if they would like to participate. If a subject is unable to stay after MRE to complete patency capsule procedures, the family can choose to return in the next 1-2 days to any CMH GI location with study staff to complete the procedure.
- Post Consent:
 - Subject will have lab draw for: Hemoglobin/Hematocrit (Hgb/Hct), erythrocyte sedimentation rate (ESR), Albumin.
 - Lab draw at time of standard of care IV placement for MRE if possible
 - If not possible to complete at MRE subject may have at the time of patency capsule or WCE visit.
 - If the subject has had these labs drawn for standard of care in the last 2 weeks, those values will be used in place of this lab draw
 - Patency capsule (performed as a part of the research study): A dissolvable capsule the same size as the PillCam SB capsule, with a radio frequency identification (RFID) tag (size 3mm x 13mm) packed in a lactose and barium powder. If the capsule is retained more than 80 hours it will dissolve into small pieces that can pass naturally through the GI tract after 2-5 days. Due to its ability to dissolve it is unlikely that if the capsule is retained that it will cause any further complications.
 - Subject will swallow the capsule. They will then follow the below schedule.
 - 0-2 hours nothing to eat or drink
 - 2-4 hours clear liquid only
 - 4+ hours may eat and drink freely
 - Miralax dose at the time the child can eat: Less than 5 years of age 2 doses (34 grams), 5-10 years of age 3 doses (51 grams), greater than 10 years of age 4 doses (68 grams).
 - *Due to the age range of subjects in the study they will likely be in school during the time they are enrolled in the study. To allow for greater flexibility for families. The patency capsule can be swallowed at home or*

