8. STATISTICAL CONSIDERATIONS

Measures

1. Detection rate of upper intestinal lesions in known IBD – CD undergoing WCE vs radiologic modality.
2. Definitive diagnosis of SB involvement of patients undergoing WCE vs radiologic modality in indeterminate IBD.
3. Complication rate for WCE vs 1st radiologic testing
4. Retention rate of WCE
5. The Crohn's disease activity index and its relation with the findings on both modalities
6. Lewis score on WCE

Sample size determination

With a sample size of 34 participants we will have 80% power probability to detect the 23 % difference in IBD small intestinal MRE findings and WCE detection rate similar to previously reported pediatric studies [11]. This determination uses a Chi-Square test and a two-sided significance level of 0.05. Subjects whose MRE results show findings that are contraindicated with WCE will be considered screen failures. We anticipate around 20% screen failure rate and intend to recruit 40 subjects to obtain a sample size of 34 evaluable subjects.

Data Analyses

The disease activity detection rate of MRE and WCE will be compared using McNemar's test and Chi square test. The sensitivity and specificity of both tests will be calculated based on a gold standard of classifying disease activity using Crohn's disease activity index (CDAI). The person correlation coefficient or spearman rank correlation coefficient

will be utilized to assess agreement between lewis capsule endoscopy score and CDAI. All p values will be 2 sided with statistical significance evaluated at 0.5 alpha level.

HUMAN SUBJECTS

Institutional Review Board (IRB) Review and Informed Consent

This protocol, and any subsequent modifications, will be reviewed and approved by the Pediatric IRB at The Children's Mercy Hospital & Clinics.

We request a partial Waiver of HIPAA Authorization for pre-recruitment activities.

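### WCE and MRE are read with history and laboratory data, then scored against a clinical activity index, so their sensitivity and specificity may be biased, probably upward

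*Combined protocol and SAP*

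**What the plan says.** Section 6 (Data Collection Procedures) sets the masking rule for both tests: "The examiners of WCE and MRE will be blinded to each other's findings but will be aware of the patient's history and laboratory data". Section 3 calls the study single blinded and adds no detail.

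Secondary objective 2 in Section 1 concerns patients with "active vs. inactive CD and IC as defined by the Pediatric Crohn's disease activity index". Section 8 (Data Analyses) makes that index the reference: "The sensitivity and specificity of both tests will be calculated based on a gold standard of classifying disease activity".

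On the reads themselves, Section 6 has the principal investigator read WCE first, with two gastroenterologists confirming. A WCE study is called "positive if clear abnormalities of the SB mucosa (i.e. ulcerations, erosions, polyps, vascular lesions, and bleeding lesions) were observed". For MRE, "one radiologist will retrospectively review the MRE for all subjects to provide a consistent assessment of the extent". No positive/negative rule is given for MRE, and the plan does not say whether the clinical report or this re-read is the MRE result analysed.

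On the index, no section says who scores it, when, or with what knowledge of the tests. The record review gathers "medical and surgical history, imaging results initial disease presentation and patient current clinical status" together.

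**The concern.** Sensitivity and specificity measure how well a test agrees with a reference. If the reader already holds information close to that reference, part of the agreement comes from the information and not from the image. A reader who knows that a child is clinically unwell may settle a borderline finding as positive, and one who knows that the child is well may settle it as negative. The same can happen in reverse if the person scoring the index has seen the imaging.

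At stake is the meaning of the figures reported under secondary objective 2. Read as the accuracy of the image, they may be too favourable. The comparison of the two tests' accuracy could also shift if one test is influenced more than the other. The error is systematic, so a larger sample would not remove it.

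**Working it through.** **1. The chain of statements.** Section 6 gives readers history and laboratory data. Sections 1 and 8 grade their reads against a clinical activity index. The first is a stated rule, not a silence. The silence concerns two further matters: masking of readers to the index, and masking of the index scorer to the tests.

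**2. Room for judgement.** The WCE rule counts erosions as positive but treats erythematous spots and mucosal breaks as non-specific, so borderline reads remain. The rule describes mucosal findings, and MRE has no stated rule.

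**3. Figures available.** The plan gives no expected sensitivity, specificity or precision for secondary objective 2, so there is no figure to reproduce. Section 8's 34 evaluable patients were set for the primary aim; 34 is used here only as a denominator. The split into active and inactive is not given, so 10, 17 or 24 active is assumed.

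**4. Weight of one read.** One changed read moves sensitivity by 1/a and specificity by 1/(34 − a), where a is the number active:
- a = 10: 1/10 = 10.0 points; 1/24 = 4.2 points
- a = 17: 1/17 = 5.9 points for each
- a = 24: 1/24 = 4.2 points; 1/10 = 10.0 points

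**5. Pull toward the index.** Let s be the masked sensitivity, f the share of wrong calls moved to the index, and g the share of right calls moved away (f and g are assumed). The observed value is s + f(1 − s) − gs. With f = 10–20% and g = 0:
- s = 50%: 55–60%
- s = 70%: 73–76%
- s = 90%: 91–92%

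The same formula applies to specificity. At s = 70% the rise is cancelled when g = f(1 − s)/s, that is 0.10 × 0.30/0.70 = 4.3% or 0.20 × 0.30/0.70 = 8.6%.

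**6. Lean toward positive calls only.** Suppose instead that a share h of all negative calls becomes positive, whatever the index says. Sensitivity becomes s + h(1 − s), and specificity c becomes c(1 − h). With s = c = 70% and h = 10–20% (assumed), sensitivity reads 73–76%, while specificity falls to 0.70 × 0.90 = 63% or 0.70 × 0.80 = 56%. The direction is therefore not fixed for both figures.

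**7. Comparison of the tests.** An equal pull of f = 10–20% shrinks a true gap of 90% against 70% from 20 points to (1 − f) × 20 = 18–16 points. A pull on one test alone separates two equal 70% tests by 0.30f = 3–6 points.

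**8. Sampling error for scale.** Wilson 95% intervals near 70% are 40–89% for 7/10, 47–87% for 12/17 and 51–85% for 17/24. All are wider than the shifts in step 5.

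**The case against.** The strongest reply is that this is an open design choice. MRE is standard of care, WCE results go into the medical record as they would in practice, and clinicians read images with the history at hand. Accuracy of the image together with clinical information is a legitimate target. That stands. What is missing is a statement that this is the target.

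Several stronger readings are tempting, and the documents do not support them:
- *Readers see the index score.* Section 6 says only history and laboratory data. Access to the score is an inference from silence.
- *The study labs are part of the index.* No section lists its components. The overlap with haemoglobin/haematocrit, ESR and albumin is an inference, although no other use of these labs is stated.
- *Late laboratory draws bias the index.* Section 5 says of the labs: "If not possible to complete at MRE subject may have at the time of patency capsule or WCE visit". Knowing the images cannot change a measured value, and a late draw may mean that the first MRE reader did not have it.
- *MRE is pulled more than WCE.* The absence of an MRE rule leaves more room, but a larger pull is conjecture.

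There are also partial safeguards: two gastroenterologists confirm each WCE read, and software calculates the Lewis score. These limit individual discretion but do not mask anyone.

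Finally, full masking of WCE may be out of reach. The principal investigator reads first, Section 5 lets a study doctor discuss the MRE result with the family before WCE, and symptoms are asked about at the WCE visit. The documents do not say that these are the same person, nor do they rule it out. This objection stands and limits what can be asked of the WCE reads.

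**Conclusion.** The concern holds in a limited form. As written, the plan leaves both tests' reads open to clinical information related to the reference they are graded against, and it states no masking of the index scorer. Agreement with the index may be biased, probably upward. A reader might infer that sensitivity and specificity must both be inflated; step 6 shows why that does not follow.

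The size cannot be computed from the documents. The 3–6 point illustration at 70% rests entirely on assumed values of f and g, and it lies within sampling error for every assumed split of the 34 patients. The point concerns secondary objective 2. A reader might extend it to the primary aim, but the paired comparison of MRE and WCE yield does not use the index as its reference. It is worth correcting because the central part of the correction uses a reader and a read already planned.

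**What to change.** In Section 6, replace the sentence on what examiners know with text stating that:
1. the planned single-radiologist MRE re-read is done without laboratory values, symptom history, the activity index or the WCE result, records a positive/negative call, and is the MRE result used for sensitivity and specificity;
2. the activity index is scored without knowledge of the MRE or WCE result;
3. where feasible, each WCE reader records and locks the research read before opening laboratory values, symptoms or the index, and any prior knowledge of these or of the MRE result is recorded.

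Clinical reports are completed with full history, as now. Where a read cannot be masked, or has already been done, report sensitivity and specificity as those of image plus clinical information and state this as a limitation.

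The cost is modest: one extra field on the MRE re-read, a two-stage WCE read, and an index scorer kept away from the test results. The WCE clinical report may come slightly later, and the research reads will be less like routine practice. WCE masking will remain incomplete, both for the reasons given under the objection and because Sections 6 and 8 have the WCE software hold the patient's name, MRN and date of birth, so it depends on readers not opening the chart before locking the read.
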